11.5.2 Success Rates – Actual versus Theoretical

Fit acceptance (0=Unacceptable, 1=Acceptable) will be analysed using a generalized linear mixed model with a binary distribution and a logit link function. Lens type, period, and the lens by period interaction will be included as fixed effects and subject will be included as a random effect. The proportion of eyes with acceptable lens fit with each lens type will be calculated with 95% confidence intervals. These confidence intervals will be compared to the theoretical success rates.

If the incidence rate is too low or there are problems with the convergence of the above model, the method of Wilson⁵ will be used to evaluate the confidence intervals.

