3 STUDY DESIGN & RATIONALE

This will be a one-day, double-masked, randomised, repeated measures study. Each subject will wear the three lens types (Acuvue® OASYS® with HydraClear Plus™ in two base curves and 1-Day Oasys with HydraLuxe™ in one base curve). A total of six lenses will therefore be worn by each subject (3 per eye).

An attempt will be made to include subjects who have large corneas or have previously demonstrated loose / tight fitting contact lenses since eyes with larger corneas tend to be less successful in contact lens fitting.

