3.1 Randomisation

Subjects will wear each of the three lens types bilaterally in random succession. A random number generator (Microsoft Excel) will determine the randomisation of lenses to subjects, which is then incorporated into the Randomisation Log.

The randomised assignment of subjects will be performed at the first assessment prior to the first randomised lens fitting. The following must be ensured prior to randomisation:

- Informed consent has been obtained
- Subjects meet all inclusion / exclusion criteria
- Subject history and baseline information have been collected

Subjects who are discontinued may be replaced in order to achieve the targeted minimum number of cohort subjects, but the ID number will not be reused.

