5 STUDY POPULATION

5.1 Number of Subjects

Approx. 50 subjects (40-60 subjects) who fulfil the inclusion criteria will be fitted with study contact lenses.

In order to fully explore the hypothesis an attempt will be made to include subjects who have an HVID of >11.75mm, Corneal Diameter of >13.75mm, or who have exhibited 'loose' or 'tight' lens fittings in previous studies.

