11.1 Sample Size Rationale

A sample size of 60 subjects showing a 90% success rate would give an 80% confidence interval of $\pm 5.0\%$. This would statistically differentiate success rates of 85% and 95%.

A sample size of 60 is sufficient to detect a mean difference of 5 (0-100) in tightness, or 0.2 mm in corneal overlap assuming the standard deviation of the mean differences in Table 2 below and assuming $\alpha=0.05$ with a power of 95%.

Table 2: Sample Size Justification:

	Sample Size	
	Tightness (0-100)	Corneal overlap (mm)
Mean of paired difference	5	0.2
SD of paired difference	10	0.4
Minimum sample size per group	42	42

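### The lens-by-period interaction in the binary model of Section 11.5.2 makes it fragile at 40–50 subjects or success near 95%, and the Wilson fallback makes no allowance for paired eyes

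*Protocol*

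**What the plan says.** Section 11.5.2 of the Protocol analyses fit acceptance (0/1) with a generalised linear mixed model, logit link, subject as random effect. On the fixed effects it says: "Lens type, period, and the lens by period interaction will be included as fixed effects". For each lens it reports the proportion of eyes with an acceptable fit and a 95% interval, which is set against the theoretical success rate. If incidence is too low or there are "problems with the convergence of the above model", the Wilson method supplies the interval. No reduced model comes between the two, and no allowance for two eyes per subject is mentioned.

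The design inputs are in other sections. Section 3: "A total of six lenses will therefore be worn by each subject (3 per eye"). Section 3.1: "Subjects will wear each of the three lens types bilaterally in random succession". Section 5.1: "Approx. 50 subjects (40-60 subjects) who fulfil the inclusion criteria will be fitted with study contact lenses". Section 11.1 illustrates precision thus: "A sample size of 60 subjects showing a 90% success rate would give an 80% confidence interval of" ±5.0%, and adds: "This would statistically differentiate success rates of 85% and 95"%.

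Section 11.5.1 models the same outcome with lens type as the only fixed effect. None of the hypotheses in Section 2.1 concerns period or a lens-by-period effect.

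**The concern.** The interaction gives the binary model nine fixed-effect cell parameters for an outcome in which failures are expected to be few. When every eye in a cell is a success, the maximum-likelihood logit for that cell is infinite. The lens mean is an average over three period logits, so one infinite cell spoils that lens's estimate.

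One of two things then follows. The software may report a fit with an enormous standard error, giving an interval that is compatible with almost any theoretical rate. Or the convergence rule triggers and Wilson intervals are used. The reported unit is eyes, and a Wilson interval that counts the two eyes of a subject as independent is too narrow when they are positively correlated. Hypothesis ii is judged by comparing these intervals with the model's predictions, so either defect bears directly on that conclusion.

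**Working it through.** **Plan's own figure.** The 80% half-width at 90% success with 60 units is 1.2816 × √(0.9 × 0.1 / 60) = 1.2816 × 0.0387 = 4.96% (Wilson 5.01%). The stated ±5.0% reproduces with 60 independent units.

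**Inputs.** N = 60, and 40 and 50 (Sections 11.1, 5.1). Success 90%, with 85% and 95% as the surrounding values (Section 11.1). Two eyes per subject per period, three lenses, three periods (Sections 3, 3.1). The protocol gives no within-subject or inter-eye correlation, so these are assumed and shown as ranges.

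**Expected failures per cell.** Eyes per cell = 2N/3; failures = (2N/3)(1 − p).
- N = 60: 40 eyes, so 6.0 failures at 85%, 4.0 at 90%, 2.0 at 95%.
- N = 50, 90%: 33.3 × 0.10 = 3.3.
- N = 40, 90%: 26.7 × 0.10 = 2.7.

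**Chance of a failure-free cell, independent eyes and equal cells.** P(any of 9) = 1 − (1 − p^(2N/3))^9.
- N = 60, 90%: 0.9^40 = 0.0148, giving 12.5%.
- N = 50, 90%: 0.9^33.3 = 0.0298, giving 24%.
- N = 40, 90%: 0.9^26.7 = 0.0602, giving 43%.
- N = 60, 95%: 0.95^40 = 0.1285, giving 71%.
- N = 60, 85%: 0.85^40 = 0.0015, giving 1.3%.

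**With subject correlation.** Simulation with a logit-normal subject effect, SD 0 to 2.5:

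| N | Success rates | P(at least one failure-free cell) |
|---|---|---|
| 60 | 85% all lenses | about 2–7% |
| 60 | 90% all lenses | about 12–27% |
| 50 | 90% all lenses | about 27–39% |
| 40 | 90% all lenses | about 44–59% |
| 60 | 85/90/95% by lens | about 37–49% |
| 60 | 95% all lenses | about 72–76% |

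These figures move by a few points with simulation error and with how evenly the lens orders fall. Unrestricted random orders make the cells unequal and raise the chance somewhat.

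**Does the model actually fail?** Maximum-likelihood fits, 120 datasets per scenario, subject SD 1.5 and 2.5. A diverging estimate counts as not estimable.

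| N | Success rates | With interaction | Lens + period only |
|---|---|---|---|
| 60 | 90% | 18–23% | 0–1% |
| 60 | 85/90/95% | 48–53% | 0–1% |
| 60 | 95% | about 77% | 1–2% |
| 40 | 90% | 48–71% | 2–4% |
| 40 | 95% | 93–95% | 12–23% |

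Divergence follows the failure-free cells closely. Without the interaction each lens has 120 × 0.10 = 12 expected failures at N = 60 and 90%.

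**Wilson fallback on 120 eyes from 60 subjects, true rate 90%.** The true standard error exceeds the independent-eyes value by √(1 + ρ), where ρ is the inter-eye correlation. At ρ = 0.5 that is √1.5 = 1.22, and the effective sample size is 120/1.5 = 80. Simulated coverage of the nominal 95% interval is 95.4% at ρ = 0, and about 92%, 90% and 88% at ρ = 0.3, 0.5 and 0.7.

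**Which proportion.** With a subject SD of 1, a population-averaged 90% requires an intercept of 2.564. Back-transforming at a random effect of zero gives 1/(1 + e^(−2.564)) = 92.9%. With an SD of 2 it gives 96.8%.

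**The case against.** The main objection is that four failures per cell does not mean the model usually fails. That stands. At 60 subjects and 90% success, roughly three quarters or more of trials would have no failure-free cell, and at 85% nearly all would be free of one. Recruitment favours large corneas and previous loose or tight fits, which Section 3 describes as less successful in fitting, so 85% is a realistic case. The 90% in Section 11.1 illustrates interval width and is not a forecast. A reader might infer that the model will generally be inestimable; the protocol's figures support this only at smaller enrolment or if one or more lenses approach 95%.

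Three other stronger readings are not supported:
- That the analysis would be swapped at will after the data are seen. Section 11.5.2 names the fallback and its triggers in advance. Nor does an empty cell necessarily trigger it.
- That the reported proportion is biased as planned. The section does not say that it is back-transformed at a random effect of zero. The 92.9% and 96.8% show what that choice would do under assumed SDs.
- That Section 11.5.3 has the same defect. Its models are linear, so separation cannot occur.

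It can also be said that lens-by-period is a conventional crossover check, and that the unit for the Wilson step may be left to the SAP. Both are fair. The check does not have to sit inside the model that produces the estimates, however. The Wilson step would be sound on one eye per subject, but the text reports a proportion of eyes.

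**Conclusion.** The point holds as a conditional weakness of Section 11.5.2. The interaction serves no stated hypothesis and makes the binary model fragile. The risk is a minority one at 60 subjects and 90% success. It is roughly a quarter to three fifths at 40–50 subjects and 90%, a third to a half at 60 subjects with lenses at 85/90/95%, and about three quarters at 60 subjects if every lens is at 95%. All of these lie within the protocol's own enrolment range and success rates. When it occurs, hypothesis ii rests on an uninformative interval or on a fallback with no stated allowance for paired eyes, whose coverage falls several points short under moderate inter-eye correlation.

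The sizes depend on assumed correlations. The cell counts do not, and the direction of the coverage loss requires only positive inter-eye correlation.

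**What to change.** In Section 11.5.2 only:
1. Fit lens type and period as main effects with subject as random effect. Show success by lens and period as a descriptive check.
2. Make the fallback a subject-clustered interval, for example Wilson with effective sample size 120/(1 + ρ̂) at 60 subjects, or a subject-level bootstrap. If a lens has no failures at all, the bootstrap collapses to zero width and ρ cannot be estimated. In that case use the number of subjects as the effective sample size, which is the ρ = 1 limit (120/2 = 60).
3. State that the proportion compared with theory is the population-averaged one.

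The fallback still matters after step 1, since 12–23% of main-effects fits diverged at 40 subjects with 95% success for all lenses.

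The cost is a change of wording before the data are seen. The one statistical downside is that a true lens-by-period interaction would be averaged over instead of modelled. Section 11.5.3 needs no change.

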2.1 Hypotheses

The following hypotheses will be tested:

- i. The fitting success rate for a combination of two senofilcon A designs is greater than for a single design when fitted to a population skewed to larger corneas.
- ii. The fitting success rates for senofilcon A designs are equivalent to those predicted by the Young model.
- iii. The fitting characteristics (tightness, corneal overlap) for senofilcon A designs are equivalent to those predicted by the Young model.

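### Section 11.5.2's Wilson fallback makes no allowance for two eyes per subject, so computed on eyes its 95% interval is too narrow whenever fellow eyes are positively correlated

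*Protocol*

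**What the plan says.** Protocol section 3.1 puts every lens type in both eyes of each subject: "Subjects will wear each of the three lens types bilaterally in random succession". Each per-lens proportion therefore contains two fellow eyes from the same person.

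Section 11.5.2 specifies a logistic mixed model for fit acceptance: "Lens type, period, and the lens by period interaction will be included as fixed effects and subject will be included as a random effect". It then fixes the reported quantity and the level: "The proportion of eyes with acceptable lens fit with each lens type will be calculated with 95% confidence intervals". The use follows: "These confidence intervals will be compared to the theoretical success rates". The hypothesis served is ii in section 2.1: "The fitting success rates for senofilcon A designs are equivalent to those predicted by the Young model".

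The fallback applies "If the incidence rate is too low or there are problems with the convergence of the above model". In that case Wilson's method, cited to a 1927 paper, provides the intervals. The section states no effective sample size, cluster-adjusted variance, choice of one eye or per-subject outcome.

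The precision statement in section 11.1 counts subjects: "A sample size of 60 subjects showing a 90% success rate would give an 80% confidence interval of" ±5.0%.

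**The concern.** Wilson's interval is built for a single binomial count of independent observations. Two eyes of one person fitted with the same lens are unlikely to be independent, and the protocol's own random subject effect provides for that dependence. Applied to the proportion of eyes with the number of eyes as denominator, the fallback drops the provision just when the model that carried it has failed.

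Hypothesis ii is one of three co-primary hypotheses in section 11.2, all to be met at a 5% level, and these intervals are what is set against the theoretical rates. The protocol does not spell out the decision rule, so there are two cases:

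- If disagreement is declared when the interval excludes the theoretical rate, too narrow an interval declares disagreement too often.
- If equivalence is judged by the interval lying inside limits, too narrow an interval favours false agreement.

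In both cases the nominal 5% is not the real error rate.

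**Working it through.** **Inputs.** Two eyes per subject for each lens type (section 3.1); 40-60 subjects, so 80-120 eyes per lens type (section 5.1); 90% success as the planning rate (section 11.1); 95% level and eyes as the unit (section 11.5.2). The fellow-eye correlation r is not given and is assumed over 0 to 0.7.

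**1. The plan's own figure.** Half-width = z·√(p(1−p)/n), with z = 1.2816 for 80% confidence.
- n = 60 subjects: 1.2816·√(0.09/60) = 4.96%, which reproduces the stated ±5.0%.
- n = 120 eyes: 1.2816·√(0.09/120) = 3.51%, which does not.

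The planned precision thus rests on one observation per subject.

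**2. Effect of pairing.** The variance of the proportion of eyes is p(1−p)(1+r)/(2N). Wilson on 2N eyes assumes p(1−p)/(2N). The matching effective sample size is 2N/(1+r).

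**3. The interval at 108/120 eyes.** Wilson: centre (p + z²/2n)/(1 + z²/n); half-width z·√(p(1−p)/n + z²/4n²)/(1 + z²/n); z = 1.96.
- n = 120: centre (0.9 + 0.0160)/1.0320 = 0.8876; half-width 1.96·√(0.00075 + 0.0000667)/1.0320 = 0.0543.
- n = 60: centre (0.9 + 0.0320)/1.0640 = 0.8759; half-width 1.96·√(0.0015 + 0.000267)/1.0640 = 0.0774.

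| r | effective n | 95% interval | width (points) |
|---|---|---|---|
| 0 (eyes as independent) | 120 | 83.3-94.2% | 10.9 |
| 0.1 | 109.1 | 82.9-94.3% | 11.4 |
| 0.3 | 92.3 | 82.2-94.6% | 12.4 |
| 0.5 | 80 | 81.5-94.8% | 13.4 |
| 0.7 | 70.6 | 80.8-95.1% | 14.2 |
| 1 (subjects) | 60 | 79.9-95.3% | 15.5 |

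The ratio of the last width to the first is 15.49/10.85 = 1.43.

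**4. Coverage.** For each subject the number of acceptable eyes is two, one or none with probabilities p² + rp(1−p), 2p(1−p)(1−r) and (1−p)² + rp(1−p). At p = 0.9 and r = 0.5 these are 0.855, 0.09 and 0.055. Summing over 60 subjects gives the exact distribution of the count, and coverage is the probability that the Wilson interval on 120 eyes contains p.

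| r | p = 90% | average, 85-95% success | range, 96-99% success |
|---|---|---|---|
| 0 | 95.4% | about 95% | no shortfall |
| 0.1 | 94.3% | about 94% | no shortfall |
| 0.3 | 92.1% | about 92% | 94.4-95.2% |
| 0.5 | 89.8% | about 89% | 92.4-94.1% |
| 0.7 | 87.5% | about 87% | 89.8-93.0% |

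The 85-95% column is relevant if the model fails to converge at ordinary success rates. The 96-99% column is relevant to the low-incidence trigger, taken here to mean few failures: 120 × 0.04 = 4.8 down to 120 × 0.01 = 1.2 expected failed eyes.

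**5. Candidate corrections.** Wilson with n = number of subjects covers about 96-99% over these rates and r = 0 to 0.7. The alternative is Wilson on eyes/(1+r), with r estimated as 1 − d/(2p(1−p)), where d is the share of subjects whose two eyes disagree. This depends heavily on the data when failures are few. With one failed eye in 60 subjects, d = 1/60 = 0.01667 and 2p(1−p) = 2·(119/120)·(1/120) = 0.01653, so the estimate is slightly negative and is cut to 0. If r is set to 1 when there are no failures, the lower limits are:
- no failures, n = 60: 60/(60 + 3.84) = 94.0%
- one failed eye, n = 120: 95.4%
- two failed eyes in different subjects, n = 120: 94.1%

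A perfect record would then get the worst lower limit of the three.

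**The case against.** The best defence is that section 11.5.2 never says how Wilson is to be computed. It names no denominator for the fallback. The reference to eyes sits in a paragraph whose model already carries a subject effect, section 11.4 allows summaries by subject or by eye, and section 11.1 counts subjects. A statistical analysis plan, not available here, could specify an adjusted version. This stands in part: nothing shows an intention to treat eyes as independent, and a reader should not infer one. But the section does pair a named unit (eyes) with a named single-proportion method, and following it literally gives the wrong width.

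Second, the harm is doubly conditional: the fallback must be used, and r must be material. This stands. How often the fallback would be used is unknown, and at r = 0.1 the loss is about one point at most.

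Third, the larger losses belong to 85-95% success, whereas sparse failures mean higher success rates. This also stands. The shortfall at 96-99% success is negligible at r = 0.3 and about 1 to 3 points at r = 0.5.

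A reader might go further and infer that the test of hypothesis ii as a whole is invalid, or that section 11.5.1 has the same defect. The documents do not support either. The mixed model is the main analysis and accounts for the subject. Section 11.5.1 repeats the fallback sentence but names no proportion of eyes, so the unit there is open.

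**Conclusion.** The point holds for the fallback in section 11.5.2, read as Wilson on all eyes, and for nothing beyond it. For any positive r the nominal 95% interval is too narrow. With 60 subjects, average coverage is about 92% to 87% for r = 0.3 to 0.7 at 85-95% success, and between 95% and 90% over the same r at 96-99% success. If disagreement means that the interval excludes a fixed theoretical rate, which is an assumed reading, false disagreement at 85-95% success is about 6%, 8%, 11% and 13% at r = 0.1, 0.3, 0.5 and 0.7, instead of 5%; under sparse failures it is lower.

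The direction follows from the design. The size rests on an assumed r, on the correlated-pair model above and on the literal reading of the unit. The correction is worth making because it is cheap and the interval bears on a co-primary hypothesis. It is not a flaw in the main analysis.

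**What to change.** State in section 11.5.2 that, when the fallback is used, the Wilson interval is computed on the observed proportion of eyes with n equal to the number of subjects. This matches the unit behind the ±5.0% in section 11.1, needs no estimate of r from a handful of failures, and avoids the reversal shown in step 5.

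The price is conservatism: coverage of about 96-99% and, at 108/120, an interval about 43% wider than Wilson on eyes.

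If the model fails to converge while failures are numerous enough to estimate r (roughly 85-95% success), Wilson on eyes/(1+r) is a less conservative option and could be named for that case. The rule that sets r to 1 with no failures and otherwise uses the estimate should not be applied when failures are few.

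Make the same change in section 11.5.1 only if its Wilson fallback is computed on eyes.

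The cost is one or two sentences and a few lines of SAS code. Data collection, sample size and the main model do not change.

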NO. SITES:	Two sites in UK: Visioncare Research Ltd, Farnham; Aston Research Clinic, Birmingham
END POINTS:	Completion of assessment of three pairs of lenses or discontinuation.
VISITS/SCHEDULE:	One visit
PROCEDURE:	Lenses will be inserted and each pair assessed after ~30 minutes.
CLINICAL VARIABLES:	
Primary variables:
 
Lens fit: horizontal* & vertical* centration (mm), post-blink movement in primary gaze* (mm), version lag (mm), edge tightness (0-4), tightness (push-up %), horizontal corneal overlap (mm)*, diameter acceptance (mm), overall fit acceptability (0-5), fit success rate (%).
 
Corneal topography: Sim-K-readings and corneal shape factor (Medmont), horizontal HVID* (photo slit lamp) corneal sagittal height, corneal diameter (Visante OCT).
 
* From photographs / video

THEORETICAL FIT VARIABLES:	Edge strain (%), corneal overlap (mm), fit success (Yes/No) based on following criteria: Edge strain: 0-6%, Horizontal corneal overlap: 0.2-1.2mm.

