1 INTRODUCTION

Since ocular topographies vary within the population,¹ it is important that contact lens designs are selected that comfortably and successfully fit a wide range of eyes. Multiple designs generally give a wider coverage of the population than single designs. Because soft contact lenses are generally not available in a wide range of parameters, it is difficult to evaluate the effectiveness of design combinations. However, senofilcon A lenses have recently become available in multiple diameters, which offers the opportunity to explore the utility of various design combinations.

Computer modelling provides useful insights into the relationship between lens design and fit and allows an estimation of the fitting success rate for a given lens design on a given population.^{2,3} Recent calculations suggest that a combination of multiple diameter designs is likely to be more successful than multiple base curves of identical lens diameter.⁴

The main purpose of this study is to evaluate the fitting success of various combinations of senofilcon A lens designs. A secondary purpose will be to evaluate the validity of the Young soft contact lens fit model.²

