11.5.3 Fitting Characteristics – Actual versus Theoretical

The fitting characteristics will be analysed separately for tightness and corneal overlap using linear mixed models. The regression models will include the experimental design factors: lens type, period, and the lens by period interaction as fixed effects, and subject as a random effect. Comparisons will be carried out using 95% confidence intervals constructed of least-square means (LSM) from the linear mixed models.

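### Actual and theoretical fit are compared only as per-lens averages, which cannot show whether the model identifies the eyes that fit; eye-level agreement is a cheap addition

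*Protocol*

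**What the plan says.** - **Purpose.** Section 1 says "A secondary purpose will be to evaluate the validity of" the fit model. Hypotheses ii and iii in Section 2.1 are worded as equivalence of success rates, and of tightness and overlap, to the model's predictions.
- **Model output.** The Synopsis lists the theoretical variables: "Edge strain (%), corneal overlap (mm), fit success (Yes/No) based on following criteria: Edge strain: 0-6%, Horizontal corneal overlap: 0.2-1.2mm". A Yes/No result and an overlap in millimetres are naturally results for one eye with one lens.
- **Data collected.** Section 8.2.3 records corneal topography, iris diameter, sagittal height and corneal diameter at baseline. Section 8.2.4 records overlap, push-up tightness and overall fit grade, and Sections 8.2.5 and 8.2.6 repeat this for the other two pairs.
- **Success rates.** Section 11.5.2 fits a logistic mixed model with lens type, period and their interaction, plus a random subject effect. It derives the proportion of eyes with acceptable fit per lens type and then says: "These confidence intervals will be compared to the theoretical success rates".
- **Characteristics.** Section 11.5.3 uses linear mixed models with the same terms: "Comparisons will be carried out using 95% confidence intervals constructed of least-square means (LSM) from the linear mixed models".

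Neither section lists the eye's own predicted value as a term, or says that the outcome is a difference from it. Section 11.5.4 adds only unspecified post hoc analyses.

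**The concern.** A fit model can be right on average and wrong about individual eyes. The planned comparisons see only the average. If the theoretical rate falls inside the observed interval, the report may say that the model has been validated, although nothing in the analysis has tested whether the eyes predicted to fail are the eyes that failed. The study appears to collect what is needed to test that, so the information would be gathered and then left out of the stated analysis.

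An equivalence margin on the averages would not change this, because a model with the right average and no eye-level skill would still satisfy it.

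**Working it through.** **1. The plan's own figure.** Section 11.1 gives an 80% interval of ±5.0% for 90% success in 60 subjects. The simple formula gives 1.2816 × √(0.9 × 0.1 / 60) = 0.0496, so the figure reproduces. The example below uses the same 60 and 90%, treating eyes as independent, one per subject.

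**2. Same rates, different agreement.** Observed success 54/60 and predicted success 54/60, so there are 6 observed and 6 predicted failures. Let k be the number of failing eyes that the model correctly predicts to fail. Then:

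- agreement = (60 − 2(6 − k))/60
- sensitivity for failure = k/6
- specificity = (54 − (6 − k))/54
- kappa = (agreement − 0.82)/0.18, since chance agreement is 0.9² + 0.1² = 0.82

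| k | Observed / predicted rate | Agreement | Sensitivity | Specificity | Kappa |
|---|---|---|---|---|---|
| 6 | 90% / 90% | 100% | 100% | 100% | 1.00 |
| 3 | 90% / 90% | 90% | 50% | 94.4% | 0.44 |
| 0 | 90% / 90% | 80% | 0% | 88.9% | −0.11 |

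The Wilson 95% interval for 54/60 is 79.9% to 95.3%. It contains the predicted 90% in every row, so the planned comparison reads the same each time. With 120 eyes (108/120) the interval narrows to 83.3% to 94.2%, and the worst-case agreement and kappa do not change.

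**3. A model with no eye-level skill.** The k = 0 row is an extreme, so a milder case was simulated: 20,000 trials of 60 eyes, with predictions having the correct long-run rate but unrelated to the eyes.

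| True success rate | Predicted rate inside observed 95% interval | Sensitivity for failure |
|---|---|---|
| 90% | 82% | 10% |
| 80% | 82% | 20% |
| 70% | 84% | 30% |

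Sensitivity is at chance level, yet the comparison of rates looks satisfactory in more than four trials out of five.

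**4. Corneal overlap.** Section 11.1 assumes a paired-difference SD of 0.4 mm without saying what is paired. Assume that it is observed minus predicted, with mean 0 and n = 60.

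- 95% interval for the mean: 2.001 × 0.4/√60 = ±0.10 mm
- 95% limits of agreement: 1.96 × 0.4 = ±0.78 mm, a span of 1.57 mm
- model acceptance window: 1.2 − 0.2 = 1.0 mm

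The mean would look precise while the spread for single eyes exceeds the whole window. If the SD were half as large (0.2 mm), the limits would be ±0.39 mm, a span of 0.78 mm. Only an eye-level analysis would show which applies.

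**5. Tightness.** The model gives edge strain, with an acceptance range of 0–6%. The observation is push-up on a 0–100% scale. The protocol gives no conversion, so observed minus predicted is not defined for tightness and no such calculation is made here.

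**The case against.** **The hypotheses are about rates.** This is the strongest point and it stands. Section 1 also describes the model as a way to estimate a success rate for a lens design in a population, and Section 11.5.2 tests that use. A reader might infer that the plan fails to test hypothesis ii. It does not fail: the group comparison answers that hypothesis as worded. What it does not reach is the broader stated purpose of assessing validity.

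**Eye-level prediction is not stated.** Also true; it is inferred from the Yes/No output and the baseline biometry. If the theoretical rates came from a reference population instead, they would not describe a sample deliberately skewed to larger corneas, so the source needs stating in either case.

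**A separate analysis plan could add agreement measures.** It could. But the protocol already fixes per-lens intervals as the comparison, so this is more than a detail left open.

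**Stronger readings that the document does not support:**

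- Section 5.1 seeks subjects "who have exhibited 'loose' or 'tight' lens fittings in previous studies", and a reader might infer that opposite errors will cancel in the mean. Mixing loose and tight fitters does not show that the model's errors have opposite signs, and the mix is not fixed.
- A reader might infer that the paired SD in Section 11.1 goes unused. That section does not say whether the pairing is lens against lens or observed against predicted, and Section 11.5.3 does not define its response variable.
- The 5 tightness points in Section 11.1 might be taken as a pass criterion. They are a detectable difference for sizing.

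**Few failures.** With 12 failures in 120 eyes, a sensitivity of 6/12 has a Wilson 95% interval of about 25% to 75% before allowing for clustering. That limits how much sensitivity alone can decide.

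**Conclusion.** The point holds as a worthwhile, low-cost improvement; it is not an error in testing the hypotheses as worded. Per-lens proportions and means can support a statement that average rates agree. They cannot support a statement that the model identifies which eyes a lens will fit.

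The size depends on facts the protocol does not give. At 90% success with equal predicted rate, eye-level agreement can lie anywhere from 80% to 100%, and sensitivity for failure from 0% to 100%, with no change in the planned comparison. This rests on predictions being computable for each study eye and lens, and on independent eyes in the illustration. The overlap figures also assume that the tabulated SD refers to observed minus predicted.

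**What to change.** 1. **State the prediction.** Say in Section 11.5.2 that theoretical success and overlap are computed for each study eye and lens from that eye's baseline biometry.
2. **Section 11.5.2.** Compare actual and theoretical rates per lens type as a paired difference with a subject-clustered 95% interval. Report the two-by-two table of predicted against observed success, with sensitivity and specificity for failure. The table is needed as well, because the paired difference is still an average.
3. **Section 11.5.3, overlap.** Analyse observed minus predicted overlap per eye and lens; report the mean with its interval and the limits of agreement by lens type.
4. **Section 11.5.3, tightness.** Report the eye-level association of push-up with edge strain, unless a conversion between the two scales is specified.
5. **Conclusions.** Limit any conclusion from the group averages to equivalence of average rates, and base statements about model validity on the eye-level results as well.

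The cost is analysis wording and running the model for each eye; no new measurement appears necessary. The downside is a wide interval for sensitivity because failures are few, which the report should state.
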